6.6 Pre and Post-Intervention Measures

Participants who meet study criteria and who remain interested in participating in the 2 week intervention will be randomized to treatment or sham groups and undergo a baseline/ pre-intervention testing. The pre-intervention measures will be administered by a trained psychometrist or research assistant who will be blinded to group assignment (sham, real NIR stimulation).

The pre-intervention testing will take approximately 3 – 3.5 hours, and will consist of measures of executive function, recent memory, and mood. These same measures will be given after the two-week intervention has completed.

Individuals with Parkinson disease will complete the pre and post intervention visits when they are “off” their typical dopaminergic medications. This is identical to what Parkinson patients are asked to do as part of standard clinical care when seen at the UF Movement Disorders Clinic. To do so, the Parkinson patients will refrain from taking their parkinsonian medications overnight, with no dopa medication after 10:00 PM the night before. The theoretical rationale for evaluating patients when off dopamine medication is to obtain an index of the true status of their disease state.. The remainder of the protocol (i.e., screening, intervention) will be completed when participants are on their normal medications. When tested ‘off medication’, patients may experience increased slowness, tremors and stability. Because of this, they will be closely monitored and provided a wheel chair. If they become too uncomfortable they can take their medication and will be withdrawn from the study.

In previous IRB- approved studies, we have tested Parkinson patients off medication while they completed an array of cognitive, EEG, and other tasks. We have found that the tolerability was quite good and no participants dropped out of the study for the medication issue. In the current study, we are implementing testing ‘off dopa’ medications at the recommendation of the Parkinson Foundation.

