6.5 Screening Interview and Measures

Participants will be screened for inclusion/exclusion criteria. This will involve review of background and demographic information, medical and psychiatric history, current medications, and assessment of functional activities, along with screening of current cognitive

status using the MoCA or DRS-2, the HVLT-R or WMS-III Logical Memory, and other cognitive measures. Screening will be administered by the project coordinator.

Table 1: Screening & Baseline Measures

Dementia Screen	Montreal Cognitive Assessment (MoCA: Nasreddine et al., 2005) or Dementia Rating Scale (DRS); these are widely used cognitive screening measures for dementia; See text for cutoff scores for Cognitively Normal and MCI groups
Objective Memory	Hopkins Verbal Learning Test-Revised and the WMS Logical Memory Stories : delayed recall scores on these measures are used to assign participants to Cognitively Normal (CN), amnestic and nonamnestic MCI groups, or to exclude Parkinson patients; (see text)
Other Cognitive measures	Executive Function - Trailmaking Test (Optional: Wisconsin Card Sort) (optional for PD) Visuospatial - Judgement of Line Orientation (JLO) (optional for PD) Language - Boston Naming Test, Category Fluency (optional for PD) Attention & Processing Speed - Digit Span, Digit Symbol (optional for PD)
Medical	Background medical history - rule out medical conditions (i.e., neurodegenerative, TBI, etc.),
	Charlson Comorbidity : Assesses for variety of comorbid medical conditions, computes risk factor score
	List of Medications : stable medications for 3 months; rule out use of anticholinergic medications; rule out use of photo-sensitive medications within 15 days of intervention
Psychiatric	Mental Health Screen V.3 (Carroll & McGinley) - this is modification of Structured Clinical Interview for DSM-IV psychiatric disorders, both current and historical (SCID-IV, First, Spitzer, Gibbon, & Williams); Goal is to rule out major depressive disorder, schizophrenia, psychosis, current substance abuse, and other Axis 1 disorders
Reading Literacy	Wechsler Test of Adult Reading (WTAR) or the reading subtest from the Wide Range Achievement Test –IV (WRAT-IV); participant reads aloud single words in order to estimate reading level; All must read on at least an 8 th grade level

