Vision	Vision & Color Vision Screening : Basic visual acuity will be measured using a Snellen chart and color vision will be tested using Ishihara color plates.

Participants will require a **Study Partner** (e.g., spouse, family member, friend) to provide independent information about their cognitive and behavioral status. The study partner will complete structured questionnaires about the participant. Both the participant and the study partner must provide independent consent for this to take place. The requirement for a study partner is 'optional' for those individuals with Parkinson disease.

It is possible that some participants, particularly those in the MCI or Parkinson groups who are recruited through the UF Cognitive Disorders and Dementia clinics or CMNDR, may have already had some of the screening measures, cognitive tasks, and rating scales associated with the current study. If so, we will request permission to use these, rather than repeat them, if they have been completed within 2 months. We will also request permission to access relevant medical and neuroimaging records.

If a participant does not meet inclusion/exclusion criteria, they will be thanked for their participation and given information as to the reason for their screen failure. There are several reasons why a participant might fail inclusion/exclusion criteria. Some that are of particular concern are poor test performance on the dementia screening measures (MoCA or DRS), presence of current major depression, substance abuse, or psychosis (i.e., hallucinations, delusions). If any of these scenarios emerge, we will discuss with the participant and, if appropriate, we will offer a referral for additional clinical evaluation through their primary physician or a specialty health care provider. Should individuals report suicidal ideation, the PI or co-investigators will meet with the participant to assess risk and refer for further evaluation

or treatment if necessary. With participant permission, we will provide results of our screening to their health care provider and/or them or a family member. As mentioned above, the project team is experienced in diagnosis and treatment of mood/cognitive disorders.

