6.6.2 Recent Memory Tasks [AVLT, Arena Task, MST]

The recent memory measures include a verbal word list learning task (AVLT), a spatial navigation and learning measure (ARENA), and an object recognition memory task (MST). During post-intervention, the memory measure given as part of screening (Logical Memory Stories) will be repeated.

6.6.2a. Description of the Auditory Verbal Learning Test (AVLT): The AVLT is a word list learning task that assesses learning, proactive interference, along with retention and recognition over 30 minute delays (Rey, 1964; Schmidt, 1996). It is widely used in clinical settings and is similar to other word list learning tasks, except that the individual items are not semantically related to each other. Thus, participants must impose their own unique strategies in order to optimize learning. The AVLT consists of two 15 item lists, with List A given over 5 trials, followed by one presentation of List B, with subsequent immediate recall of List B, then List A. Later 30 minute recall and recognition of List A are obtained. The primary dependent variables for this task are overall learning, the degree of proactive interference, and delayed recall after 30 minutes.

6.6.2b. Description of Computerized Arena Task (Laurance et al., 2012): This is a task of spatial memory and navigation that has been linked to hippocampal function and is a human analogue to the Morris water maze used in animal studies. At UF, this task has been used in other IRB-approved studies with older adults (the VITAL study), those with Essential tremor, those with mild cognitive impairment and Alzheimer's disease.

[figure not shown]
The task is given on a computer and participants are trained in the use of a joystick or direction pad before beginning the task. Participants must navigate in a virtual, 3-D room displayed on a computer screen. They must start from different positions to find an invisible target on the

floor as quickly and efficiently as possible. Shown below are sample walls of the virtual room. The overall goal is to find a 'hidden target' on the floor of the arena.

[figure not shown]
The participant uses either a direction pad or joystick to navigate this "arena".

Navigation is constrained to a circular "arena" designed to look like a pool of water (the blue on the pictures above). The arena is bordered by a low wall and is in its entirety located in a perfectly square room, with each of the four

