For individuals with Parkinson disease, there is an additional potential discomfort. The PD participants may experience some increase in their symptoms (i.e., increased slowness, tremor, rigidity) when they are tested during the "off medication" state. This is similar to what occurs during their routine clinical evaluation at the Movement Disorders Clinic, when they are asked to come to their clinic appointment after being off their Parkinson medication overnight. For our research study, care will be taken to ensure that the Parkinson patients are transported by wheelchair when necessary and that they are accompanied by a member of the study team. They will be told that if they become too uncomfortable, then they should go ahead and take their medication.

It is possible that there are unknown risks for participating in this study. Individuals will be asked about side effects at each visit and encouraged to share information about subjective changes.

13. Possible Benefits

Cognitive and mood benefits cannot be guaranteed. However, it is possible that some participants may experience cognitive and mood benefits that may include improved memory, executive function, and mood. It is possible that individuals may experience some improvements solely due to expectations.

14. Conflict of Interest

No conflict of interest exists for the investigators of this protocol.

REFERENCES

- Barrett, D. W., & Gonzalez-Lima, F. (2013). Transcranial infrared laser stimulation produces beneficial cognitive and emotional effects in humans. *Neuroscience*, 230, 13–23. doi:10.1016/j.neuroscience.2012.11.016
- Beck, A. T., Steer, R. A., Ball, R., & Ranieri, W. (1996). Comparison of Beck Depression Inventories 1A and II in psychiatric outpatients. *Journal of Personality Assessment*, 67(3), 588–597.
- Chen, A. C. H., Huang, Y. Y., Arany, P. R., & Hamblin, M. R. (2009). *Role of reactive oxygen species in low-level light therapy*. Proceedings of the SPIE, 7165, Mechanisms for Low-Light Therapy IV, 716502. doi:10.1117/12.814890.

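### In the Parkinson cohort, Logical Memory is scheduled on medication before the intervention and off medication after it, so its change score spans two medication states; the arm comparison is not biased

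*Protocol*

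**What the plan says.** - **Medication state.** Protocol section 6.6: "Individuals with Parkinson disease will complete the pre and post intervention visits when they are" off their dopaminergic drugs. The same paragraph adds: "The remainder of the protocol (i.e., screening, intervention) will be completed when participants are on their normal medications". Screening is thus on medication; the Baseline and Follow-up assessments are off.
- **When Logical Memory is given.** Section 6.6.2: "During post-intervention, the memory measure given as part of screening (Logical Memory Stories) will be repeated". Table 2 agrees. The row that Logical Memory shares with the HVLT-R is marked under Screening and Follow-up, and its Baseline cell is empty.
- **Why it comes at screening.** Section 6.4c sets a floor on delayed paragraph recall for Parkinson participants, and Table 1 lists delayed recall among the scores used "or to exclude Parkinson patients". The test has to precede the Baseline visit.
- **Outcome status.** Section 7.1 does not name Logical Memory. It falls among the other memory measures, which are secondary.
- **Cohort and allocation.** Section 7.2.a plans 20 Parkinson participants per arm, allocated 1:1 within the cohort. Section 7.3 analyses each cohort separately.
- **Analysis.** The SAP takes post minus baseline change, compares arms by independent t-test, and uses Cohen's d to help choose cognitive measures for later trials.

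**The concern.** The protocol's stated reason for off-medication testing is "to obtain an index of the true status of their disease state". The Logical Memory pre score does not serve that purpose, and no reason is given for the exception. Post minus pre for this test mixes whatever happened over two weeks with whatever overnight withdrawal does to story recall.

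Two things are at stake. First, a reader who looks at change within the active arm, or at the Occasion term in the protocol's ANOVA, would see the medication shift and could take it for decline or for lack of benefit. Second, the SAP uses d to guide the choice of measures. If withdrawal adds patient-to-patient variation to one test's change score and not to the others', that test could look weaker for a reason unrelated to its sensitivity to treatment.

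**Working it through.** The documents give no medication effect, SD, retest correlation or power for this measure, so there is no stated figure to reproduce. The schedule and the allocation come from the documents. Every correlation and shift below is an assumption.

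**1. Schedule (sections 6.6, 6.6.1 and 6.6.2, Table 2)**

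| Measure | Pre score | Post score |
|---|---|---|
| Logical Memory | Screening, on medication | Follow-up, off medication |
| AVLT, Arena, MST, NIH Examiner, Stroop | Baseline, off medication | Follow-up, off medication |

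**2. Is the arm comparison biased?** Let s be the mean on-to-off shift and t the treatment effect. Expected change is s + t in the active arm and s in the sham arm. The difference is t, whatever s is.

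A simulation confirms this (20 per arm, 20,000 trials per setting, pre-post correlation 0.70 before any withdrawal variation, s of 0, -0.5 or -1 SD, withdrawal-response SD of 0 or 0.5):
- With no true effect, the mean arm difference was -0.003 to 0.001 and the t-test rejected in 0.048 to 0.051 of trials.
- With a true effect of 0.5 SD, the mean estimate was 0.497 to 0.502.

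**3. Is within-arm change readable?** No. With s = -0.5 SD and a true benefit of +0.5 SD, the active arm changes by about -0.5 + 0.5 = 0 and the sham arm by -0.5.

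**4. What happens to the change-score variance?** Take unit variances and an off/off correlation of 0.70. Change variance is 2(1 - 0.70) = 0.60.
- *If everyone responds alike to withdrawal*, it stays at 0.60 and nothing is lost.
- *If the on/off correlation drops to r*, the variance ratio is (1 - r)/(1 - 0.70). For r = 0.65, 0.60 and 0.50 this is 1.167, 1.333 and 1.667. A d standardised by the SD of change is multiplied by 0.926, 0.866 and 0.775.
- *If withdrawal instead adds independent variation with SD 0.5*, change variance is 0.60 + 0.25 = 0.85. The SD is 0.92 against 0.77, and d is multiplied by sqrt(0.60/0.85) = 0.84.

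For scale, the standard error of d at d = 0.5 with 20 per arm is sqrt(2/20 + 0.25/80) = 0.32. The largest loss above is 0.5 × (1 - 0.775) = 0.11.

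**5. ANCOVA on the follow-up score against raw change, for Logical Memory itself**
- *Equal variances:* (1 - r²)/[2(1 - r)] = (1 + r)/2. For r = 0.70, 0.65, 0.60 and 0.50 this is 0.85, 0.825, 0.80 and 0.75.
- *Added withdrawal variation, SD 0.63:* post variance is 1 + 0.397 = 1.397 and covariance 0.70. ANCOVA residual variance is 1.397 - 0.49 = 0.907. Change variance is 0.60 + 0.397 = 0.997. The ratio is 0.91.

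These are large-sample ratios. Estimating the slope with n = 20 per arm inflates the ANCOVA variance by about 1 + 1/(2n - 4) = 37/36 = 1.03 under normality, so some gain remains throughout.

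**6. Does adjustment make Logical Memory comparable with the other tests?** No. With ANCOVA on both, the residual variance relative to a test taken off medication twice is (1 - 0.50²)/(1 - 0.70²) = 0.75/0.51 = 1.47 at r = 0.50. With added variation of SD 0.63 it is 0.907/0.51 = 1.78. The ratio is 1 only if withdrawal affects everyone alike.

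**The case against.** **No planned estimate is wrong.** The hypotheses are relative to sham, and the SAP contains only between-arm tests. This stands, and it is why the point is minor. A reader might infer from the mismatch that the Parkinson treatment comparison is biased. It is not: the shift is common to both randomised arms and cancels.

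**Within-arm change was never clean.** Parkinson participants are selected on screening paragraph recall, which invites regression to the mean, and repeating the stories invites practice effects. Both points are right. Matching the medication state would remove one contaminant of several, which supports leaving within-arm change uninterpreted.

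**The loss in d stacks assumptions.** The SAP lists no measures, so it is not known that a Logical Memory d was computed or used. It also does not say which SD standardises d; with the screening-score SD, the losses in step 4 would not arise. Effect sizes across tests differ in reliability and practice effects anyway. This stands. The step 4 figures illustrate a mechanism and do not estimate a loss.

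**Section 6.6 says the same measures are given before and after.** That describes the pre-intervention battery. Section 6.6.2 identifies Logical Memory as a screening test, and Table 2 agrees.

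**Some pre scores may really be off medication.** Section 6.5 says of earlier clinic results that "we will request permission to use these, rather than repeat them, if they have been completed within 2 months", and section 12 describes Movement Disorders Clinic visits "when they are asked to come to their clinic appointment after being off their Parkinson medication overnight". A reader might infer a substantial mix of states. The documents do not say that reusable cognitive tests were done at those visits, and section 6.5 also names the cognitive disorders clinics, so no share can be put on it. Anyone with an off-medication pre score would simply not have the mismatch.

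**Trail Making.** A reader might extend the point to it, because section 6.6.1 calls it a screening measure. Table 2 places it at Baseline and Follow-up, so a mismatch is not established.

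**Conclusion.** The scheduling mismatch is real and rests on the text alone: section 6.6, section 6.6.2 and Table 2 agree. It concerns one memory measure, secondary by implication, in at most 40 people. The AVLT, Arena and NIH Examiner, which carry the co-primary cognitive outcomes, are unaffected.

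Bias in the randomised comparison from this source is zero, given that both arms follow the same schedule. What remains is that within-arm change on Logical Memory cannot be read as change over the intervention. Its precision, and its d if scaled by the SD of change, may also be lower than with matched states. The size of that loss cannot be estimated from the documents and may be nil. The point is minor: it calls for a better analysis of this one measure and a sentence in the report.

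**What to change.** For Logical Memory in the Parkinson cohort:

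1. Compare follow-up scores between arms by ANCOVA with the screening score as covariate, in place of the raw change-score t-test. This uses data already collected. If results have been seen, label the analysis as added afterwards and show the t-test beside it.
2. Do not interpret within-arm change on this measure.
3. State in one sentence that its pre score was scheduled on medication and its post score off, so its d is not like-for-like with measures taken off medication twice. ANCOVA does not remove the need for this sentence.

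The cost is one model and one sentence.

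Only if enrolment is still open, consider giving the test again at the off-medication Baseline visit, using that as the pre score and keeping the screening score for eligibility. That adds a story recall with its delay to a visit of 3 to 3.5 hours, at which the protocol says of participants: "If they become too uncomfortable they can take their medication and will be withdrawn from the study". It also adds one practice exposure, equal in both arms. The SAP is written in the past tense, so this option has probably passed.

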6.6.1 Executive Measures [NIH Examiner, Stroop]

The executive measures include the NIH Examiner, a computerized battery consisting of 9 individuals subtasks described below, and a measures of cognitive inhibition (Stroop task). During post-intervention, an executive measure given as part of screening (Trail Making Test) will be repeated.

6.6.1a Description of the NIH Examiner: The National Institutes of Health Executive abilities: Methods for Neurobehavioral Evaluation and Research (Kramer et al., 2012). The NIH Examiner is a computer based battery that involves nine tasks of frontal-executive function and takes around 45 minutes to complete. Funding for development of the NIH Examiner was provided by NINDS in 2005 to develop sensitive, domain-specific tasks of fronto-executive function. The NIH Examiner consists of 9 individual tasks that can be combined into three domain specific scores: *Cognitive Control, Working Memory, and Fluency*. An overall *Executive Composite* score can also be computed (Kramer et al., 2014). In the current study, the **dependent variable for the primary aim will be the “executive composite”**

score calculated from the tasks within the NIH Examiner. Described below are each of the 9 tasks of the battery.

1. *Dot Counting (working memory)*: Participants look at a mixed array of green circles, blue circles, and blue squares. They are asked to count all of the blue circles and remember the final total, before counting the blue circles on new displays. The number of new displays increases from two to seven over a total of six experimental trials. The dependent variable is total correct score over trials 1-6, which contributes to the Executive Composite and the Working Memory factor scores.
2. *N-back (working memory)*: Participants view a series of white squares that appear in different locations on a black screen. In the 1-back trials, participants are required to remember the location of squares and compare the location of each new square to the previous square. In the 2- back trials, participants are required to compare each new square location to the location of the square two trials before. The 2-back will only be administered if sufficient performance is reached on the 1-back (computerized adaptive testing). The 1-back consists of 30 trials total while the 2-back consists of 90 trials. Discriminability (d-prime) is calculated as the difference between the z-transforms of the hit rate and the false positive rate. The dependent variables are the 1-back and 2-back d-prime scores and contribute to the Working Memory factor score and the Executive Composite.
3. *Flanker (inhibition)*: In this task, participants view a row of five arrows presented at the center of the screen and then indicate the direction of the center arrow using the arrow keyboard keys. In some sets of trials, all arrows point in the same direction (congruent); in other sets of trials, the center arrow points in the opposite direction of the rest of the arrows (incongruent). Reaction times are typically longer on the incongruent trials. A total of 48 trials are administered. Total accuracy score and reaction time scores on the incongruent trials are calculated and added together to create the total flanker score. The dependent variable is the total flanker score, which contributes to the Executive Composite and the Cognitive Control factor score.
4. *Continuous Performance Test (inhibition)*: Participants are asked to press a button when they see a five-pointed star, and not respond when they see any other shape. A total of 100 trials are presented, 80% consisting of the five-pointed star. The dependent variable is the total number of false alarm errors made on the stimuli. This variable contributes to Executive Composite and Cognitive Control factor scores.
5. *Anti-saccades (inhibition)*: In this task, participants are asked to watch a moving dot on the computer screen and move their eyes upon presentation of a laterally presented stimulus. Some trials involve moving eyes in the direction of the presented stimulus (prosaccade, 10 trials), and some involve moving eyes in the opposite direction (anti-saccade, 40 trials). The dependent variable is the total number of correct anti-saccade trials, which contributes to the Executive Composite and Cognitive Control factor scores.
6. *Set Shifting (set-shifting)*: Participants are required to match a stimulus on the top of the screen to one of two stimuli located in the lower corners of the screen. Stimuli are matched either based on color or shape depending on the cue. There are three tasks: Task A involves matching stimuli based on shape (homogenous; 20 trials), Task B involves matching stimuli based on color (homogenous; 20 trials), and Task C alternates between matching stimuli based on shape and color (heterogeneous; 64 trials; 32 shape, 32 color). Both reaction time score and accuracy scores are calculated across all blocks. These two scores are summed to create the dependent variable, a total set shifting score. This total set shifting score is used to calculate the Executive Composite and the Cognitive Control factor scores.
7. *Phonemic Fluency (fluency)*: In this task, participants are asked to generate as many words that begin with a particular letter of the alphabet. The task is timed for one minute and participants are given two different letters (F and L) for which they must generate words. The dependent variables are the total number of correct words generated on F and L trials, which contribute to the Executive Composite and Fluency Factor scores.
8. *Category Fluency (fluency)*: This task is similar to “phonemic fluency”. However, participants are

asked to generate as many words possible that belong to a particular category. This task is timed for one minute and participants are given two categories (animals and vegetables) for which they must name items. The dependent variables are the total number of correct words generated on animal and vegetable trials, which contribute to the Executive Composite and Fluency Factor scores.

9. **Unstructured Task** (planning): In this task, participants are presented with three booklets, each containing five pages of puzzles. Puzzles are cognitively simple but may take anywhere from 4 to 60 seconds to complete, and are associated with a specific point value. Participants are given six minutes to complete puzzles and are required to use judgment and planning skills in order to earn as many points as possible. The dependent variable is the total number of points earned during the 6 minutes. The score on this task is not factored in to the Executive Composite or the factor scores.

6.6.1b. Description of the Stroop (Golden version). This version of the Stroop is a standard task given as part of the typical neuropsychological exam and is pre-approved by the IRB. It involves 3 parts: Word Reading, Color Naming, and Color-Word Interference. During Word Reading, a participant reads the words (red, blue, green) typed in black ink on a white page, vertically. Final trial score is total number of words read in 45". During Color Naming, the participant rapidly names the color patches (red, green, blue) that are arrayed on a card. Final trial score is total number of patches accurately identified in 45". During the Color-Word Interference condition, a word (i.e., Red) is printed in color ink that differs in meaning from the meaning of the written word. The participant's task is to name the ink color of the word, and inhibit reading the word. Final trial score is total number of items identified over 45". The **dependent variable** is the cognitive inhibition score, which is based on the Color-Word interference score, taking into account performance on the 2 baseline trials.

